## 1. Introduction & rationale

The number and proportion of older people is increasing in the UK and many other countries as people are living longer. However, while lifespan is increasing, healthspan is not keeping pace and many older people live with significant illness. Ageing ultimately leads to the loss of functional capacity in many body systems including the cardiovascular, musculoskeletal, osteoarticular and neuroendocrine. A hallmark feature of ageing is immune decline, termed immunosenescence, with the functional decline of the innate and adaptive immune systems resulting in compromised immunity [1-3]. Paradoxically, in parallel there is an elevation in systemic inflammation with ageing, a phenomenon termed inflammageing [4, 5]. Inflammageing and its associated conditions including cardiovascular disease, metabolic diseases, sarcopenia and osteoporosis, some cancers and possibly dementia, make significant contributions to morbidity, poor quality of life, mortality and increased social and health care costs in older people. Furthermore, immunosenescence increases susceptibility to infections contributing to illness and mortality [6]. Importantly, these immune changes also limit responses to public health measures like influenza vaccination [7, 8]. The coronavirus pandemic has highlighted the vulnerability of older people to infections; this vulnerability is likely to be at least in part due to age-related immune changes. Thus, there is an urgent need to understand and overcome the drivers of age-related immune changes that cause ill health.

The intestinal microbiota has an influence on host health by, for example, acting through direct and indirect effects on the host immune system and inflammatory response [9, 10]. The structural complexity and functional capability of the intestinal microbiota decline with ageing [11-14]. How this occurs and the nature of the relationship between changes in the microbiota, the onset of low-grade inflammation, declining gastrointestinal tract function, and immunosenescence in older people are not well described. The loss of intestinal barrier function in older people which can result in translocation of bacterial endotoxins and whole bacteria into the bloodstream is a plausible link between intestinal dysbiosis and inflammaging, and is consistent with the concept that manipulation of the intestinal microbiota may be of therapeutic benefit in older people [15]. Nutritional approaches may be used to modify the intestinal microbiota [16, 17] and to support the immune system including regulating inflammation [18]. Vitamin D is important in this regard and having sufficient vitamin D is likely to be important in maintaining innate and cell-mediated immunity and preventing low-grade inflammation [19-25]. Vitamin D levels are low in the UK population [26] and vitamin D levels among British adults are inversely associated with infection risk [27], suggesting that the influence of low vitamin D status on immune competence is a public health problem. There are a number of reports of low vitamin D status being linked to risk of coronavirus infection and severity of COVID-19 [28-30]. The link between low vitamin D status in older people and immunosenescence and inflammaging requires further exploration. Intriguingly, high dose vitamin D supplements have also been shown to alter the faecal microbiota in animal models [31] and in humans [32, 33]. The intestinal microbiota may also be manipulated through oral intake of probiotics. *Lactobacillus plantarum* is a probiotic organism which has been shown to survive passage through the gastrointestinal tract and colonise in the intestines in humans, with the TIFN101 strain exhibiting the strongest persistence in the gut [33]. *L. plantarum* TIFN101 has been shown to positively affect the immune system by supporting the maintenance of immune cells [34] and stimulating memory responses and antigen presentation [35], supporting intestinal barrier function [36], and protecting against intestinal inflammation by mediating inflammatory signaling molecules in humans [37]. However, the use of this organism is yet to be investigated in older adults in whom

there are changes in the intestinal microbiota [11-14], immune decline [1-3], and elevated inflammation [4, 5].

Robust investigation of diet-microbiota interactions in the context of age-related immune decline and inflammaging requires a cross-disciplinary approach and reliable experimental tools. A consortium of expert researchers from the Universities of Southampton, Birmingham, and East Anglia (The Quadram Institute) have come together to collaborate on this trial, which is funded by the Medical Research Council. The trial is a 2 x 2 factorial trial testing the impact of vitamin D, a probiotic organism, and a combination of the two on immunosenescence, inflammation and the intestinal microbiome in older participants. The interventions will be calcifediol (also known as calcidiol, 25-hydroxycholecalciferol, or 25-hydroxyvitamin D3) to be used at a dose of 10 µg/day vs placebo, *Lactobacillus plantarum* TIFN101 at a daily dose of 5 x 10^9 colony forming units (cfu) vs placebo, and a combination of the two vs placebo over a period of 3 months. Calcifediol has been demonstrated to elevate plasma 25-hydroxyvitamin D3 concentrations more effectively than cholecalciferol [38-40]:

Time course of unadjusted serum 25(OH)D concentration (nmol/L) in healthy older adults.

(Taken from Ref. 39)

Study products will be provided gratis by DSM Nutritional Products; an MTA is in place to cover this.

## 2. Objective

The objectives of this study are to identify the effect of vitamin D (calcifediol) and *Lactobacillus plantarum* TIFN101 alone and together on the intestinal microbiota, markers of immune function and inflammation and other health-related markers (blood lipids, body composition, muscle strength) in older adults.

## **Inclusion and exclusion criteria**

### Inclusion criteria

1. Community dwelling males and females aged 60+ years
2. Body mass index 18.5-35 kg/m^2
3. Willing to adhere to the study protocol
4. Able to provide written informed consent

### Exclusion criteria

[figure not shown]
1. Living in a care or nursing home
2. Diagnosed with diabetes or other metabolic and endocrine disorders
3. Presence of active gastrointestinal disease (coeliac disease, Crohn's disease, diagnosed IBD etc.), autoimmune disease, or inflammatory disease (lupus, rheumatoid arthritis, multiple sclerosis), COPD, active cancer or current cancer treatment or having had cancer within the last year, having had a heart attack or other cardiac event within the last year
4. Use of steroid inhalers, or use of prescribed medicine to control inflammation (e.g. non-steroidal anti-inflammatory drugs; NSAIDs) or prescribed vitamin D or calcium+vitamin D or regular use of over-the-counter NSAIDs
5. Use of dietary supplements (will allow a 4-week washout period)
6. Use of probiotic drinks or yoghurts (will allow a 4-week washout period)
7. Blood donation in the previous 3 months
8. Participation in any other clinical trial in the previous 3 months

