## Recruitment

Participants will be sought through poster advertisements; articles in the media (newsletters, newspapers, radio, university project specific social media pages, targeted social media click advertisements); posters and email within the University of Southampton and University Hospital Southampton NHS Foundation Trust; contacting those on a GDPR compliant database held by the University Hospital Southampton; through contact with Age UK and other organisations particularly relevant to older people; and via local GP surgeries who will act as Participant Identification Centres (these will be identified with the help of the Wessex clinical research network (CRN)). Individuals who are interested will contact the research team by telephone. They will then be sent the Participant Information Sheet. They will be able to contact the researcher to confirm their interest. If they do not contact the researcher within 7 days they will be contacted by the researcher to see if they remain interested in the study. Those individuals who indicate interest in the study will answer a small number of questions to ascertain whether they are likely to meet the inclusion/exclusion criteria (screening questionnaire). If so, an appointment will be made for them to attend visit 1 (V1) at the NIHR Wellcome Trust Clinical Research Facility at Southampton General Hospital.

### Visit 1

Participants will attend the NIHR Clinical Research Facility at Southampton General Hospital in the morning (between 8 and 10:30 am) in the fasted state (no food or drink apart from water from 9 pm the night before). Participants will be given the opportunity to discuss the study and have any questions answered. If they are happy to be enrolled, they will be asked to sign an Informed Consent Form.

At this visit, participant's height, weight, mid-arm upper circumference, waist and hip circumferences and blood pressure will be measured. In addition, their body composition will be measured using a Tanita bioelectric impedance apparatus and grip strength will be measured using a hand grip dynamometer taking the maximum of three readings with each hand. ~60 mL blood will be collected to provide whole blood, serum and plasma.

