After blood collection, participants will be given breakfast (orange juice, toast and jam, tea or coffee). Following consumption of breakfast, participant's diet will be assessed using the widely used EPIC Food Frequency Questionnaire, their quality of life will be assessed using EQ5D5L and their physical activity will be assessed using PASE. Participants will then be randomised to one of four groups (vitamin D (calcifediol, 10 µg/day), probiotic (*Lactobacillus plantarum* TIFN101 (5 x 10^9 cfu/day)), vitamin D + probiotic, or placebo) and will receive 3 months supply along with a diary to record that they have taken their supplement each day. Blinding, randomisation, and supplement packaging will be completed by individuals independent of the researchers involved in the study. Participants will be randomised stratified by sex to ensure equal numbers of males and females in each treatment group.

Participants will also take away materials for collection of faecal and urine samples. They will be provided with a pack and instructions for collecting a faecal sample and 3 urine samples at home within one week of V1. Two urine samples will be collected on weekdays (one per day) and one urine sample will be collected at a weekend or first thing on a Monday morning. Participants will be asked to complete a 24 hr food diary using the online tool 'intake 24' or by completing a

paper diary 24 hr prior to collecting each urine sample. Participants will be asked to keep the urine samples in their home fridge until all 3 samples have been collected. Participants will be asked to collect a faecal sample within 24 hours of the last urine collection. Participants will be asked to either return their samples to the Clinical Research Facility in person or to contact the researcher once samples are available who will travel to their home to collect the samples or will arrange for them to be collected by courier.

At the end of V1 participants will be provided with their supplements and instructed to start taking these once they have produced their faecal sample and three urine samples. Participants will receive instructions on taking their supplements and will record this daily use in a paper diary.

Participants will be contacted every 4 weeks by the researcher (at week 4 and week 8) and will be requested to bring unused supplements to their end of study clinic visit (visit 2; week 12). These will be used to assess compliance.

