#### 4. Variables and analyses

The primary outcomes measured will be vitamin D status (measured as 25-hydroxyvitamin D3 in serum), colonisation of the probiotic organism (measured as numbers of *L. plantarum* in faeces), and serum CRP concentration (measured with a high sensitivity kit).

In addition, the following will be measured as secondary outcomes:

1. Immune cell phenotypes
2. Inflammatory markers
3. Faecal microbiome taxonomy
4. Weight, body mass index, body fat mass, body lean mass, hip circumference, waist:hip ratio
5. Grip strength
6. Dietary intake (from food frequency questionnaire)
7. Quality of life (questionnaire)
8. Physical activity (questionnaire)
9. Respiratory symptoms (questionnaire)
10. Blood glucose, insulin, HOMA-IR
11. Blood lipids (total, LDL and HDL cholesterol, triglycerides)
12. Blood adipokines (leptin, adiponectin, leptin/adiponectin ratio, visfatin and resistin)
13. Blood markers of intestinal barrier integrity
14. Blood PTH and calcium, as markers of vitamin D homeostasis
15. Faecal metabolome
16. Urinary metabolome

Serum calcium and plasma parathyroid hormone will be measured as these relate to vitamin D status and action.

Full blood count will be conducted to obtain absolute numbers of different types of immune cells.

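### Antibiotic use is neither addressed in the exclusion criteria nor covered by any stated recording procedure, although faecal L. plantarum is a primary outcome

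*Protocol*

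**What the plan says.** Section 2 of the protocol sets out to study the two products "alone and together on the intestinal microbiota, markers of immune function and inflammation". Section 4 names, among three primary outcomes, "colonisation of the probiotic organism (measured as numbers of *L. plantarum* in faeces", and lists "Faecal microbiome taxonomy" and the faecal and urinary metabolomes as secondary outcomes.

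The exclusion list has eight items, numbered without a gap. Those on medicines and products are:

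- Item 4: "Use of steroid inhalers, or use of prescribed medicine to control inflammation (e.g. non-steroidal anti-inflammatory drugs; NSAIDs", continuing with prescribed vitamin D and regular over-the-counter NSAIDs.
- Item 5: dietary supplements, with a 4-week washout.
- Item 6: "Use of probiotic drinks or yoghurts (will allow a 4-week washout period".

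Antibiotics appear neither in this list nor elsewhere in the protocol text.

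Section 3 describes the data collection. At screening, interested people "will answer a small number of questions to ascertain whether they are likely to meet the inclusion/exclusion criteria (screening questionnaire". The participant diary is for daily supplement intake. During treatment, "Participants will be contacted every 4 weeks by the researcher (at week 4 and week 8", with no question on medicines stated. WURSS-21 records respiratory symptoms on days when there are any. No record of concomitant medication is described at V1, at V2 or in between.

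**The concern.** The protocol accepts that the gut flora must be shielded from outside influences, since it washes out probiotic yoghurts. It is silent on a drug class that acts directly on bacteria, in a trial where one product is itself a live bacterium.

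Two situations follow from the text as written. A person who has just finished a course meets the criteria and may give a disturbed baseline faecal sample. A participant in a probiotic arm who is treated shortly before the V2 sample may show few or no L. plantarum, with nothing in the stated data collection to explain it.

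The protocol makes such exposure foreseeable: its introduction describes older people as more susceptible to infection. It also cites an inverse association between vitamin D levels and infection risk. If calcifediol changed infections, antibiotic use could differ between arms, and without a record a direct effect on the microbiota could not be told apart from an effect through fewer courses.

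Eligibility and data collection belong in the protocol. A statistical analysis plan cannot restore data that were never collected.

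**Working it through.** **1. The plan's own sizing (section 5).** Inputs: difference 70 − 45 = 25 nmol/l, SD 25, p < 0.01 (taken as two-sided), power 95%.

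n per level = 2 × (2.576 + 1.645)² × (25/25)² ≈ 35.6, so 36. Power at 36 is 95.2%. Enrolment: 72 / 0.70 = 102.9, so 103; the stated 104 fits four arms of 26. For CRP (mean 6.3, SD 2.2, 20% reduction = 1.26, two-sided 0.05), power at 36 per group is 68% against the stated 70%. The sizing reproduces.

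For colonisation, section 5 gives no effect, SD, detection rate or power. It also gives no antibiotic rate. No figure for the harm can therefore be derived from the document, and steps 2 to 4 are illustrations on labelled assumptions.

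**2. Colonisation as detected or not detected.** Assumptions: 36 v 36; a share q exposed close enough to the V2 sample to matter; detection D in unexposed probiotic takers; 10% in exposed takers and in controls; Fisher's exact test, two-sided 0.05.

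Detection in the probiotic groups = (1 − q) × D + q × 0.10.

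| D | q = 0 | q = 5% | q = 20% |
|---|---|---|---|
| 50% | 50.0%, power 95.9% | 48.0%, power 94.0% | 42.0%, power 84.6% |
| 60% | 60.0%, power 99.6% | 57.5%, power 99.2% | 50.0%, power 95.9% |
| 70% | 70.0%, power 99.98% | 67.0%, power 99.95% | 58.0%, power 99.3% |

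The detection difference shrinks by q × (D − 0.10): from 0.05 × 0.40 = 2 points to 0.20 × 0.60 = 12 points. If only 1-2% are exposed in the relevant window, power at D = 50% is 95.5-95.2%.

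**3. A continuous outcome, as section 4 words it (numbers in faeces).** Assumption: the effect is wholly lost in a share f, so the mean difference becomes (1 − f) times its full value. With 36 per level and two-sided 0.05, a contrast with 80% power falls to 75.9% (f = 5%), 71.3% (10%) or 61.1% (20%). One with 95% power falls to 92.8%, 90.0% or 82.2%. The N needed rises by 1/(1 − f)²: 1.11, 1.23 and 1.56.

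**4. Added noise in other faecal outcomes.** Assumption: exposure shifts a measure by k SD in a share q of participants. Variance becomes 1 + q(1 − q)k².

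- k = 1: 1.05 (q = 5%) to 1.16 (q = 20%). The 72 completers carry the information of 72/1.0475 ≈ 69 to 72/1.16 ≈ 62.
- k = 2: 1.19 to 1.64, equivalent to 72/1.19 ≈ 61 down to 72/1.64 ≈ 44.

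**5. Where a course could still come to light.** Section 6.1 defines an adverse event broadly, section 6.4 registers all of them from the screening visit to trial completion, and section 6.3 weighs concomitant therapy when judging causality. An infection that led to a course could appear there. None of these passages asks for the drug or its dates, or for courses not tied to a reported event. Courses completed before the screening visit fall outside the register.

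**The case against.** The best case against is that the harm is small and partly conjectural.

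- **Primary outcome.** With detection of 60% or more in takers, power stays near 96% or higher even with 20% exposed. This stands.
- **Exposure.** Participants are community-dwelling and clinically healthy, with COPD, active gastrointestinal disease and active cancer excluded. The product is taken daily for three months, so the organism is re-supplied after a mid-study course, and mainly courses near the V2 sample should matter. Nothing in the protocol supports 20% in such a window. This stands as a reason to treat that figure as an upper illustration.
- **Endpoint.** The outcome is a count analysed as change by ANOVA, not detection. This is fair, and it is why step 3 is shown; there a moderate effect loses more power.
- **Records.** Case report forms and the content of the telephone contacts are not shown. This too stands: the protocol supports saying that recording is not stated, not that it will not happen.

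A reader might go further and infer that the probiotic effect is diluted, that the comparison is biased, or that no check will be possible at all. The document supports none of these. Dilution depends on an exposure rate and an effect loss that it does not give. Randomisation balances antibiotic use arising before treatment on average, and any later difference between arms would be a consequence of treatment, not a bias in the comparison. The adverse event register may reveal some courses.

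What the objection does not remove is the omission. The list as written admits recently treated people, and an incidental record supports neither adjustment for chance imbalance nor a complete sensitivity analysis.

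**Conclusion.** The point holds as an omission in eligibility and data collection. The exclusions control probiotic foods and supplements but not recent antibiotic use, and no stated procedure records courses during follow-up, although "colonisation of the probiotic organism" is a primary outcome.

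The consequence is possible attenuation of the probiotic effect and extra noise in the microbiome and metabolome outcomes, neither of which could be assessed systematically. Its size is unknown. On the assumptions in step 2 the loss of power for detection runs from practically nothing (70% detection) to 11 percentage points (50% detection, 20% exposed). For a moderate continuous contrast with 80% power it is about 4 to 19 points for 5-20% exposed, if the effect is wholly lost in them. All exposure rates, detection rates and shifts are assumptions. The trial's validity is not in question; this is a cheap improvement, worth making before recruitment because the information is largely unrecoverable afterwards.

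**What to change.** 1. Add recent systemic antibiotic use before V1 to the exclusion criteria, with a washout after which V1 can be rebooked. The length is for the sponsor to set and justify; the 4 weeks already used in items 5 and 6 is the protocol's own precedent.
2. Record any antibiotic course with start and stop dates at V1, at the week-4 and week-8 contacts and at V2. The baseline faecal sample is produced at home after V1, so the week-4 question should cover the days between V1 and that sample.
3. Keep all randomised participants in the primary analysis whatever their antibiotic use. Use the record for a sensitivity analysis of the faecal outcomes, for example leaving out participants with a course within a stated window before a faecal sample. Its details can sit in the statistical analysis plan. Because a course during follow-up is a post-randomisation event, this analysis supports the primary result and does not replace it.
4. Report antibiotic use by arm.

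Cost: one eligibility line and one dated question at contacts that already take place. The downside is that a few V1 visits are delayed by the washout. Nobody's medical treatment is restricted.

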## **3. Study design and participant schedule**

All procedures involving human participants will be approved by a relevant NHS Research Ethics Committee. This study will be conducted according to the guidelines established in the Declaration of Helsinki. The study will be registered at [www-controlled-trials.com](http://www-controlled-trials.com).

The study will be a 2 x 2 factorial double-blind randomised, placebo-controlled trial carried out with clinically healthy older adults (aged 60 years and above). Participants will be assessed at baseline, take daily supplements for 3 months, then return for further assessment and conclude the study (see Figure 1 and Figure 2).

Figure 1. Overview of the study plan and of participant flow through the study

## Recruitment

Participants will be sought through poster advertisements; articles in the media (newsletters, newspapers, radio, university project specific social media pages, targeted social media click advertisements); posters and email within the University of Southampton and University Hospital Southampton NHS Foundation Trust; contacting those on a GDPR compliant database held by the University Hospital Southampton; through contact with Age UK and other organisations particularly relevant to older people; and via local GP surgeries who will act as Participant Identification Centres (these will be identified with the help of the Wessex clinical research network (CRN)). Individuals who are interested will contact the research team by telephone. They will then be sent the Participant Information Sheet. They will be able to contact the researcher to confirm their interest. If they do not contact the researcher within 7 days they will be contacted by the researcher to see if they remain interested in the study. Those individuals who indicate interest in the study will answer a small number of questions to ascertain whether they are likely to meet the inclusion/exclusion criteria (screening questionnaire). If so, an appointment will be made for them to attend visit 1 (V1) at the NIHR Wellcome Trust Clinical Research Facility at Southampton General Hospital.

### Visit 1

Participants will attend the NIHR Clinical Research Facility at Southampton General Hospital in the morning (between 8 and 10:30 am) in the fasted state (no food or drink apart from water from 9 pm the night before). Participants will be given the opportunity to discuss the study and have any questions answered. If they are happy to be enrolled, they will be asked to sign an Informed Consent Form.

At this visit, participant's height, weight, mid-arm upper circumference, waist and hip circumferences and blood pressure will be measured. In addition, their body composition will be measured using a Tanita bioelectric impedance apparatus and grip strength will be measured using a hand grip dynamometer taking the maximum of three readings with each hand. ~60 mL blood will be collected to provide whole blood, serum and plasma.

After blood collection, participants will be given breakfast (orange juice, toast and jam, tea or coffee). Following consumption of breakfast, participant's diet will be assessed using the widely used EPIC Food Frequency Questionnaire, their quality of life will be assessed using EQ5D5L and their physical activity will be assessed using PASE. Participants will then be randomised to one of four groups (vitamin D (calcifediol, 10 µg/day), probiotic (*Lactobacillus plantarum* TIFN101 (5 x 10^9 cfu/day)), vitamin D + probiotic, or placebo) and will receive 3 months supply along with a diary to record that they have taken their supplement each day. Blinding, randomisation, and supplement packaging will be completed by individuals independent of the researchers involved in the study. Participants will be randomised stratified by sex to ensure equal numbers of males and females in each treatment group.

Participants will also take away materials for collection of faecal and urine samples. They will be provided with a pack and instructions for collecting a faecal sample and 3 urine samples at home within one week of V1. Two urine samples will be collected on weekdays (one per day) and one urine sample will be collected at a weekend or first thing on a Monday morning. Participants will be asked to complete a 24 hr food diary using the online tool 'intake 24' or by completing a

paper diary 24 hr prior to collecting each urine sample. Participants will be asked to keep the urine samples in their home fridge until all 3 samples have been collected. Participants will be asked to collect a faecal sample within 24 hours of the last urine collection. Participants will be asked to either return their samples to the Clinical Research Facility in person or to contact the researcher once samples are available who will travel to their home to collect the samples or will arrange for them to be collected by courier.

At the end of V1 participants will be provided with their supplements and instructed to start taking these once they have produced their faecal sample and three urine samples. Participants will receive instructions on taking their supplements and will record this daily use in a paper diary.

Participants will be contacted every 4 weeks by the researcher (at week 4 and week 8) and will be requested to bring unused supplements to their end of study clinic visit (visit 2; week 12). These will be used to assess compliance.

Between clinic visits 1 and 2, participants will complete the daily WURSS-21 questionnaire to assess respiratory symptoms. If they have no symptoms, they will not need to complete this questionnaire.

Blood will be collected for the following measurements:

Sample	Measurement	Analysed by	Reason
Blood	Full blood count	University Hospital Southampton Chemical Pathology	Reports blood immune cell numbers (plus red cells and platelets)
Blood – Serum	TNF $\alpha$ IL-1 $\beta$ IL-1RA IL-4 IL-6 IL-8 IL-10 IL-17 IFN- $\gamma$ GM-CSF sCD14 IFN $\alpha/\beta$	University of Birmingham	Inflammatory markers
Blood - Serum	Insulin  Total cholesterol HDL- cholesterol LDL- cholesterol Triglycerides  25-hydroxyvitamin D3 Calcium	University Hospital Southampton Chemical Pathology	Glucose homeostasis  Blood lipids  Vitamin D status
Blood - Serum	Leptin Adiponectin Visfatin Resistin  CRP LPS binding protein	University of Southampton	Adipose tissue function markers  Inflammatory markers

Blood - plasma	Parathyroid hormone Glucose	University Hospital Southampton Chemical Pathology	Related to vitamin D status Glucose homeostasis
Blood - plasma	Zonulin-1 Occludin iFABP Citrulline sCD14	University of Southampton	Gut integrity markers
Blood mononuclear cells	Differentiated CD57+ve NK cells T cells PTK7+ve recent thymic emigrant cells Naïve memory T cells (CD3+ve but differential expression of CD45RA, CD28, CD57 and KLRG1) Regulatory T cells (FOXP3 and CD25+ve) B cells (CD24hi, CD38hi)	University of Birmingham	Immune cell phenotypes
Urine	Metabolome	University of Southampton	Microbiota and diet- related metabolome
Faeces	Whole genome shotgun metagenomics, and metabolomic analysis Wet/dry weight	Quadram Institute	Quantitative intestinal microbiome profiling

Volumes of blood to be collected will be as follows:

Matrix	Collection tube	Volume	Analytes
Serum	SST	~ 3.5 ml	Insulin
Serum	SST	~ 5 ml	CRP, cholesterol, HDL, LDL, triglycerides, vitamin D, calcium
Serum	SST	~ 3.5 ml	Leptin, adiponectin, visfatin, resistin
Serum	Red top serum	~ 6 ml	TNF $\alpha$ , IL-1 $\beta$ , IL-1RA, IL-4, IL-6, IL-8, IL-10, IL-17, IFN- $\gamma$ , GM-CSF, IFN $\alpha/\beta$
Blood mononuclear cells	Lithium heparin	~ 18 ml (3 x 6 ml)	Immune cell phenotypes
Plasma	Fluoride oxalate	~ 5 ml	Glucose
Plasma	EDTA	~ 6 ml	Zonulin-1, Occludin, iFABP, Citrulline, sCD14
Blood	EDTA	~ 3.5 ml	Full blood count
Plasma	Lithium heparin	~ 6 ml	Parathyroid hormone

[figure not shown]
A summary of the questionnaires to be used at each time point is as follows:

Questionnaire	V1 (baseline)	V2 (3 months)
Food frequency (EPIC and 3 x intake 24)	YES	YES
Quality of life (EQ5D5L)	YES	YES
Physical activity (PASE)	YES	YES
Respiratory symptoms (WURSS-21)	Daily between V1 and V2 (Only if participant has symptoms)	

### Visit 2

Three months ( $12 \pm 1$  weeks) after Visit 1, participants will return to the NIHR Clinical Research Facility at University Hospital Southampton for visit 2 (V2). Participants will be asked to bring a recent faecal sample and three recent urine samples with them; these will have been collected and stored in the same way as for post-V1 and again a 3 day food diary will be completed. All measurements, blood samples and questionnaires conducted at visit 1 will be repeated at visit 2.

Figure 2. Further overview of the study plan.

